6.2.4 Treatment Visits

In accordance with the Schedule of Evaluations (section 6.1 above), treatment-related measures will be collected in months 3 and 5 as follows:

- Hamilton: The Hamilton Rating Scale for Depression (HRSD)⁵⁶ (as a validated objective, interview-based assessment of depression). Atypical depression symptoms as part of the Structured Interview Guide for the Hamilton Depression Rating Scale, Seasonal Affective Disorders version (SIGH-SAD)⁶⁰ (as atypical symptoms in particular respond to light treatment⁶¹) Mania⁶² ratings (to document any clinical induction of manic symptoms by the wake or light interventions) – on ovulation night (LSH), daily on LHS+1 – LHS+2 (during intervention) and once after light treatment on LHS+8-9 (post-intervention assessment).
- Beck Depression Inventory (BDI)⁵⁷ (as a validated subjective assessment of depression) – on ovulation night (LSH), daily on LHS+1 – LHS+2 (during intervention) and once after light treatment on LHS+8-9 (post-intervention assessment),
- Beck Anxiety Inventory (BAI)⁵⁸ (as many women with PMDD report anxiety symptoms)⁶³ – on ovulation night (LSH), daily on LHS+1 – LHS+2 (during intervention) and once after light treatment on LHS+8-9 (post-intervention assessment),
- The Psychological General Well-Being Index (PGWI)⁶⁴ – on ovulation night (LSH), daily on LHS+1 – LHS+2 (during intervention) and once after light treatment on LHS+8-9 (post-intervention assessment),

- Daily mood self-ratings (DMR)⁵⁴ that include core PMDD symptoms of anxiety and irritability – collected daily on LHS+0 through LHS+2 (for wake therapy effects) and daily LHS+3 through LHS+10 (for light treatment effects),
- Pittsburgh Sleep Quality Index (PSQI)⁶⁷ to assess subjective sleep quality – once on LHS+8-9 (post-intervention assessment),
- Visual analogue scale⁶⁸ to assess subjective sleep quality – once on LHS+8-9 (post-intervention assessment),
- Ovulation testing performed for 7 days starting on menstrual cycle day 10 in months 3 and 5 to determine luteinizing hormone surge (LHS). Participants will contact Study Coordinator with their time of first menses (cycle day 1) to determine cycle day 10 and schedule appointment for collecting study forms and equipment,
- Actigraphy will be collected for 10 days starting the day of LHS to monitor baseline sleep, light and activity measures at home,
- Urine collection for 30 hrs performed between days 8-9 after LHS.

Objective assessments (HRSD) collected during intervention and post-intervention will be performed by telephone, to reduce patient burden, on the same day the patients complete the subjective assessment forms (BDI, BAI, PGWI, DMR, PSQI, sleep quality) during the times indicated above.

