2.2 Study Rationale

Interventions: The wake therapy and light interventions proposed in this application are based on our previous studies in PMDD³⁶⁻³⁹ and key published experiments by other investigators that indicate that the combined interventions are efficacious in other mood disorders after one week of treatment and maintained at 9-months follow-up.¹⁷⁻³¹ To provide optimal timing of interventions, we will administer wake therapy in the early-night vs. late-night and light pulses in the AM vs. PM at selected times in relation to sleep (within 30 min of waking and 90 min before sleep onset, respectively). These times were selected to examine phase-advance and phase-delay responses without disrupting sleep. Successful light treatment is associated with a phase-shift of the melatonin rhythm as noted by Epperson et al.⁴⁰ in a randomized trial of bright light therapy for antepartum depression and by Terman et al.⁴¹ in winter depression. In this proposal focusing on mood effects, we will administer 7 days of AM or PM light after wake and before sleep, respectively, for 60 min using a light-emitting diode (LED) device. The advantage of LEDs over conventional light boxes (fluorescent or incandescent) is that LEDs can be selected to emit light with energy concentrated at wavelengths of 450-480nm to which the human circadian system is most sensitive.⁴²⁻⁴⁴ Thus LEDs are not only more efficient, but smaller and light-weight, further enhancing patient compliance. Clinical effects on mood generally occur within 3-4 days after the onset of treatment, and expire within 3-4 days after discontinuation of treatment.^{45, 46}

A crossover treatment design will be employed to compare LWT+AM BWL vs. EWT+PM BWL responses within the same individual. As wake interventions lose effectiveness after 1 day, and light treatment effects after 3-4 days, we anticipate minimal carry-over effects of the wake plus light interventions administered a month

apart. To further ensure no carry-over effects, there will be a month of no-intervention between the 1st and 2nd treatments. Because our previous studies clearly indicated differences between PMDD and NC subjects occurred primarily in the luteal menstrual cycle phase, we will treat during this menstrual cycle phase rather than in the follicular phase.

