This design allows us to complete the studies at least two days before the next expected menstrual period. Measuring the circadian profile of urinary melatonin over 2 nights for 30+ h will allow us to assess phase, duration and amplitude changes of melatonin reflective of the underlying circadian pacemaker. In addition, we will assess phase-shift responses of melatonin to light in relation to other critical biological rhythm measures of sleep and activity. To document the sleep/wake cycle and exposure to light intensity and spectra, we will use the Actiwatch device (see description below).

[figure not shown]

Figure 1. Study flow: The luteinizing hormone surge (LHS) documents ovulation, c. menstrual cycle day (CD) 14. Urine samples for 6-sulphatoxy-melatonin (6-SMT) and reproductive hormones (RHs) will be collected for 30+ hours over 2 nights between days 8-9 after the LH surge (c. CD 22-23) in months 2,3,5; actigraphy will begin the day of LHS and continue until day 10 after the LHS (CD 14-24) of months 2,3,5; late wake therapy (LWT) or early wake therapy (EWT) will be administered at home on the night of the LHS; bright morning (AM) or evening (PM) light will be administered on days 1-7 after the LHS (CD 15-21) in a counterbalanced, cross-over design in months 3 and 5. Mood ratings (HRSD+BDI) will be collected as follows: Months 1 & 2 – once per week; Months 3 & 5 – LHS + 0 (Pre-

LWT/EWT), daily LHS +1 → LHS + 2 and once the evening after last treatment (LHS +7/8). Visual Analogue Scales (VAS) for depressed mood, anxiety, affective lability, irritability (Daily Mood Ratings)(core PMDD symptoms) collected daily during Months 1 & 2, and twice daily on LHS + 0 through LHS + 2 (for wake therapy effects) and daily LHS + 3 through LH + 10 (for light treatment effects) in Months 3 & 5. HRSD will be collected once during Month 4 and a once a month after Intervention 2 to monitor relapse.

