5. STUDY INTERVENTIONS

5.1 Interventions, Administration, and Duration

Treatment 1 will occur during the menstrual cycle immediately following the 2 menstrual cycles studied in the evaluation period. Washout will occur the following menstrual cycle, and Treatment 2 the menstrual cycle immediately following Washout. As we establish the Evaluation Period as Month 1 and Month 2, we will refer to Treatment 1 as occurring in Month 3, Washout in Month 4, and Treatment 2 in Month 5 (see section 6.1).

During Month 3, qualified participants will sign the Study Consent between cycle days 1 and 10, be randomized to treatment and receive all necessary instructions, forms and equipment to continue with the treatment phase. On the day of their luteinizing hormone (LH) surge (luteal phase), subjects will undergo a night of Late Wake Therapy (LWT) (sleep 21:00-01:00 h, followed by wake) vs. Early Wake Therapy (EWT) (wake until 03:00 h followed by sleep until 07:00 h) at home. We selected the specific wake and sleep times based on our previous work in PMDD.^{36, 37} The following day, subjects will receive the light intervention for 7 consecutive days: days 1-7 after the LH surge (approximately menstrual cycle days 15-21). Depending on their randomization schedule, subjects will receive, at home, 60 min of either AM bright white light (LED of 1350 lux at 20 inches) starting within 30 minutes of their habitual wake time (for those undergoing LWT), or PM bright white light ending 30 min before their habitual sleep onset time (for those undergoing EWT). The following Month 4 (Washout) will be a month of no intervention to prevent any carry-over effects from the Month 3 intervention affecting measures in Month 5. Mirroring Month 3 timing, in the luteal phase of Month 5, subjects will receive the alternate wake therapy (LWT or EWT) and light exposure (AM or PM) (see Fig. 1, above).

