9.5 Outcomes

9.5.1 Primary Outcome

- Treatment-Related Mood Rating Changes from Baseline (month 2) to post intervention (months 3,5) :
Mood ratings include Hamilton Rating Scale for Depression (HRSD), Beck Depression Inventory (BDI), atypical depression symptoms as part of the Structured Interview Guide for the Hamilton Depression Rating Scale, Seasonal Affective Disorders version (SIGH-SAD), Beck Anxiety Inventory (BAI), mania ratings, the Psychological General Well-Being Index (PGWI) and daily mood self-ratings (DMR) that include core PMDD symptoms of anxiety and irritability as required during diagnostic evaluation, before, during and after each wake and light intervention at the same time of day (between 15:00-17:00 h). To assess more acute effects on mood that may occur more rapidly during the wake interventions, subjects will complete DMRs twice daily beginning the evening before the wake therapy intervention and continuing until the morning after the recovery night of sleep.
- Treatment-Related Urinary 6-sulfatoxymelatonin (6-SMT) Changes from Baseline (month 2) to post intervention (months 3,5) :
6-SMT is a principal melatonin metabolite that is abundant in urine, well correlated with plasma melatonin, and serves as an excellent marker for circadian phase response.
- Treatment-related changes in objective and subjective sleep measures:
Using actigraphy, we will obtain objective measures of the sleep/wake cycle to ensure appropriate sleep/wake times during wake therapy, and during the light interventions as it is an important biological rhythm with which to compare the intervention-induced melatonin rhythm changes. To assess subjective sleep quality, we will use the Pittsburgh Sleep Quality Index (PSQI) and a visual analogue scale.

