 - e. Day after LHS (LHS+1) – commence first light treatment (for 7 days)
 - f. LHS+8 → LHS+9 – commence urine collection (30 hrs)
 - g. LHS+11 – equipment, samples and forms are returned to lab
5. Washout (Month 4)
- a. Perform clinical ratings only
6. Treatment 2 (Month 5)
- a. Record CD1 (patient will call Study Coordinator with date and to schedule pre-intervention in-office visit)
 - b. Pre-Intervention Visit – to be completed between cycle days 1 and 10:
 - i. Provide ovulation test kit
 - ii. Provide urine collection kit
 - iii. Provide Actiwatch Spectrum
 - c. Menstrual Cycle Day 10 – commence testing for LHS (7 days of testing)
 - d. Ovulation Day (LHS) – commence actigraphy recording (for 10 days)
 - commence Wake Therapy (1 night)
 - e. LHS+1 – commence first light treatment (for 7 days)
 - f. LHS+8 → LHS+9 – commence urine collection (30 hrs)
 - g. LHS+11 – equipment, samples and forms are returned to lab
7. Final Visit (can be performed at time of item 6.g. above)
- a. Review side effects to treatment and subjective global assessment of treatment effectiveness.
8. Follow-up (luteal phase in the month following Treatment 2)
- a. Perform clinical ratings per telephone.

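### Daily mood ratings on LHS+0 to LHS+2 are assigned to wake therapy, but light starts on LHS+1 and, by an afternoon rating, the morning-light arm is one session ahead

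*Combined protocol and SAP*

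**What the plan says.** Section 6.2.4 states that in the treatment months the DMR are "collected daily on LHS+0 through LHS+2 (for wake therapy effects) and daily LHS+3 through LHS+10 (for light treatment effects". The Figure 1 text in section 3 uses the same label but a different frequency: "twice daily on LHS + 0 through LHS + 2 (for wake therapy effects".

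The treatment calendar is as follows.
- **Wake therapy** "will be administered at home on the night of the LHS" (Figure 1 text).
- **Light**, Appendix I item 4: "Day after LHS (LHS+1) – commence first light treatment (for 7 days". The sessions therefore run from LHS+1 to LHS+7.
- **Morning light** (section 5.1): "starting within 30 minutes of their habitual wake time (for those undergoing LWT"), for 60 minutes.
- **Evening light** (section 5.1): "PM bright white light ending 30 min before their habitual sleep onset time (for those undergoing EWT").

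Section 9.5.1 places the mood ratings "before, during and after each wake and light intervention at the same time of day (between 15:00-17:00 h"). It also asks for twice-daily DMRs, from the evening before wake therapy to the morning after recovery sleep, in order to pick up rapid effects of the wake intervention. HRSD, BDI, BAI and PGWI are taken on LHS+0, LHS+1, LHS+2 and LHS+8-9. Section 6.2.4 describes their LHS+1 and LHS+2 values as taken during the intervention and does not call them wake ratings.

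**The concern.** A rating that is to show a wake effect should be taken after the wake night and before anything else that differs between the arms. On LHS+1 and LHS+2 that is not assured. Light has started, and because one arm receives it in the morning and the other in the evening, a rating between the two sessions finds the arms at different points in their light course. The lead belongs to LWT+AM, the arm that the hypothesis favours.

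What is at stake is the acute-effect reading announced in 9.5.1. If LWT+AM looks better on LHS+1 or LHS+2, a report that follows the stated windows would attribute this to late rather than early wake therapy, although light exposure also differed.

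**Working it through.** The documents give no figure to reproduce, so the check is a count of completed light sessions.

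**Inputs**
- Sessions on LHS+1 to LHS+7 (Appendix I; section 5.1).
- AM light starts at most 30 min after habitual waking and lasts 60 min; PM light ends 30 min before habitual sleep onset (section 5.1).
- Habitual waking no later than 09:00 and sleep onset no later than midnight (section 4.2).
- Ratings at 15:00-17:00 (section 9.5.1).

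**Does every AM session precede, and every PM session follow, an afternoon rating?**
- Latest end of AM light: 09:00 + 0:30 + 1:00 = 10:30, before 15:00.
- PM light is complete by 17:00 only if sleep onset is at or before 17:00 + 0:30 = 17:30, which is not a realistic bedtime.

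**Count at 15:00-17:00 on day LHS+d**
- d = 0: AM 0, PM 0.
- d = 1 to 7: AM = d, PM = d − 1.
- d = 8 to 10: AM 7, PM 7.

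Three assumed wake/sleep schedules (05:00/21:00, 07:00/23:00, 09:00/24:00) give the same counts.

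**DMRs at other times of day** (AM vs PM sessions completed; wake 07:00 and sleep 23:00 assumed)

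| Time of rating | LHS+1 | LHS+2 |
|---|---|---|
| Morning, before AM light | 0 vs 0 | 1 vs 1 |
| Morning, after AM light | 1 vs 0 | 2 vs 1 |
| 15:00-17:00 | 1 vs 0 | 2 vs 1 |
| Evening, before PM light | 1 vs 0 | 2 vs 1 |
| Evening, after PM light | 1 vs 1 | 2 vs 2 |

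Only one cell after the wake night is free of light in both arms: the LHS+1 morning rating taken before AM light. In the EWT+PM arm any LHS+1 morning rating meets that condition, because light comes in the evening. In the LWT+AM arm it depends on the order of form and light box, which no section fixes.

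**Can the bias be sized?** Section 2.2 says "Clinical effects on mood generally occur within 3-4 days after the onset of treatment", but gives no curve. Three assumptions show how wide the range is.
- Even build-up per session over 3-4 days: a one-session lead is worth 1/4 to 1/3 of the light effect.
- Even build-up with elapsed time (wake 07:00, sleep 23:00): first AM light at 07:00-07:30 and first PM light at 21:30, a lead of 14 to 14.5 h, or about 0.6 day. Then 0.6/4 = 0.15 and 0.6/3 = 0.20.
- Stepwise onset after day 3: close to nothing by LHS+2.

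The documents do not choose among these.

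**The case against.** The strongest case on the other side has four parts.

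1. **The split at LHS+3 has a rationale.** If light takes 3-4 days to act, little light effect is expected by LHS+2. This has weight, but it does not rescue the label. Section 2.1 says that wake therapy shortens the time light needs to work, so an early light effect is what the combined treatment predicts. Section 2.2 says that wake effects are lost after 1 day, which makes LHS+2 a poor wake rating on the plan's own terms.

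2. **The primary hypothesis is about packages.** Hypothesis 1.A (section 9.1) compares the combined treatments from baseline to post-intervention, and no wake-only test is specified. This stands. A reader might infer that the AM lead biases the main mood contrast. The documents do not support that: at LHS+8-9 both arms have had 7 sessions, and the saturated treatment-by-time model in 9.6 estimates each time point separately, so an early offset need not carry over.

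3. **The twice-daily DMRs cannot all fall at 15:00-17:00.** This stands too. For the labelled ratings the imbalance is possible rather than established; it depends on when the form is filled in. That unspecified timing is itself the defect.

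4. **HRSD, BDI, BAI and PGWI on LHS+1 and LHS+2 are not labelled as wake ratings.** Correct. They need a caution on interpretation; there is no label to correct.

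**Conclusion.** The point holds for the early ratings. The LHS+0 to LHS+2 label credits to wake therapy a period in which light has begun and, at a 15:00-17:00 rating, differs by one session between the arms (1 vs 0, then 2 vs 1). Once light has begun on LHS+1, an arm difference cannot be read as an effect of wake timing alone.

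Two stronger readings should be resisted. The one-session lead is not present at every rating: it is absent on LHS+0 and from LHS+8 onward, and on LHS+3 to LHS+7 only the DMR is collected under the 6.2.4 schedule. Nor can the bias be stated as a fixed share of the light effect, since every such figure rests on an assumed onset curve.

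The counts assume that light starts on LHS+1 as scheduled; section 10.3.3 allows a failed wake night to be repeated before light, which would delay it. The 7 vs 7 result assumes the LHS+8-9 timing in 6.2.4. The Figure 1 text gives LHS+7/8, in the evening after the last treatment; a 15:00-17:00 rating on LHS+7 would be 7 vs 6. These passages need to agree.

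**What to change.** In 6.2.4, the Figure 1 text and 9.5.1:

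- Require the already planned LHS+1 morning DMR to be completed before any light in both arms.
- Define the wake-therapy effect as the change from the LHS+0 pre-wake-therapy DMR to that rating.
- Describe all later ratings, including HRSD, BDI, BAI and PGWI on LHS+1 and LHS+2, as effects of wake therapy plus light, and do not interpret them as wake effects.
- Record the time of each DMR relative to light.
- Reconcile the DMR frequency on LHS+0 to LHS+2 (once a day in 6.2.4; twice in the Figure 1 text and 9.5.1) and the day of the post-treatment rating (LHS+7/8 in the Figure 1 text; LHS+8-9 in 6.2.4).

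Leave DMR timing from LHS+3 onward as it is. Moving those ratings to the morning would equalise session counts, but would conflict with the 15:00-17:00 rule and leave unequal time since the last session.

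The cost is protocol wording and an instruction and time field on the DMR form, with no new visits and no change in sample size. The downside is that the wake effect then rests on a single morning rating. On that morning the LWT woman has been up since about 01:00 and the EWT woman since about 07:00, so a sleep-inertia difference between the arms remains.

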6.2.5 Washout

During washout Month 4, subjects will again perform the urine toxicology screening, Hamilton, BDI, BAI and PGWI ratings (once ***during the luteal phase, around the same time in the patient's cycle as the post treatment 2 ratings were collected***).

6.2.6 Follow-up/Final Evaluation

During final visit, subjects will again perform the Hamilton, BDI, BAI and PGWI ratings (once). They will also complete the Global Assessment of Treatment Effectiveness form. Final evaluation of inclusion/exclusion criteria will be performed at this time.

After completion of the study (final visit), participants will be followed up for 1 month to monitor relapse. The Clinical Rater will telephone the patient at home during the luteal phase, around the same time in the patient's cycle as the post treatment 2 ratings were collected, to collect follow-up mood ratings (Hamilton, BDI, BAI and PGWI).

None of the subjects will be excluded from analysis, and their data will be analyzed according to the randomization scheme. Different hypotheses are included for different phases of the study. All subjects will be included in any baseline analyses regardless of their final study status. In addition to the baseline data, at least one other data point is needed in order to provide a valid estimation of a parameter for change throughout the study. The Random Regression Model was selected due to the flexibility of this method that includes all subjects with any valid data point in the analyses, as opposed to a method that is designed to examine just

the completers, such as a Repeated Measures Analysis of Variance. All subjects will be included in the analyses and we will not focus only on subjects who complete the study. Secondary analyses will be performed on data from completers. Our methods for data analyses include all subjects with any valid data points in the analyses (see Section 9.6. General Approach to Data Handling and Statistical Analyses).

7. SAFETY ASSESSMENTS

Participant safety will be monitored once an individual is enrolled for screening in the study.

7.1 Specification of Safety Parameters

Risks to patients in this protocol are low and are detailed as follows:

Affect and Anxiety:

Premenstrual symptoms may become worse leading to depression, anxiety, irritability and rarely suicidality. It is anticipated that these studies will not be greatly different from spending nights at home with some added measurements and interventions. The added measures may add some disruption and anxiety to daily schedules.

Urine Collection, Sleep/Activity:

The risks of urine collection are minimal and may include inconvenience with collection of samples and completion of forms. Sleep and activity measures are non-invasive, but may cause some skin irritation and/or discomfort on the wrist where the Actiwatch is worn.

Effects of Bright Light Treatment:

Since most of us are exposed to fluorescent light in our everyday lives, we do not anticipate that exposure to bright light per se will pose any special physical, psychological, social or legal risks. The intensity planned is less intense than bright sunlight, which normally exceeds 10,000-50,000 lux. Although 1,350 lux is more intense than common indoor room lighting during a 16-hour day, the average patient would receive more radiation from room lighting than from 1-2 hours of special lighting. Thus, the treatment is expected to be less hazardous than going for a walk or going to the beach. No special side effects apart from mild sleepiness (the patient needs to be awake for the light exposure and evening light may potentially disrupt sleep onset) are anticipated. It should be noted that sleep deprivation has been reported to benefit depressed patients. The possibility that the bright light treatment might potentiate a depressed patient's risk of switching into mania is recognized, although we have not seen this effect in previous studies of PMDD patients and we will exclude bipolar patients with mania from the study. If hypomania occurs, the light would be discontinued and appropriate referral and treatment with psychotropic medication, if needed, would be given.

Effects of Wake Therapy or Partial Sleep Deprivation:

The potential risks include fatigue. Subjects will be encouraged to stay at home the day after wake therapy or, if driving, arrange alternative transportation. In previous studies of one night of total wake therapy in PMDD patients, subjects felt energized and wished to return to work or other daily activities. Previous studies also included two consecutive nights of partial wake therapy. We anticipate fewer problems in this study with only one night of partial wake therapy.

The following risk-management procedures will be used:

Depression, Anxiety, Suicidality, Mania:

To guard against adverse effects, all subjects will have a complete psychiatric history administered by a certified clinician. By monitoring mood twice daily and by providing weekly ratings by trained clinicians, we expect to detect any problems with mood before they become severe. Known bipolar patients are excluded to reduce the risk of mania occurring. Suicidal ideation will be monitored by the Clinical Rater at the time of HRSD administration. Patients are instructed to call the Rater, Study Coordinator, Research Associate or on-call psychiatrist if these symptoms occur. Suicidal ideation will be evaluated by both the Clinical rater and PI to determine the best course of action. A licensed psychiatrist will always be on-call to subjects should any psychiatric emergency arise. If needed, patients will be referred for appropriate treatment including inpatient hospitalization if warranted.

Urine Collections:

Trained staff will instruct participants in the proper method of urine collections.

Wake Therapy:

To ensure sufficient wakefulness after the wake therapy interventions, the patient is encouraged to stay at home, not drive or operate machinery and arrange for alternate transportation, for which they will be reimbursed. To avoid the induction of mania, bipolar patients are excluded.

Actiwatch:

Equipment will be checked regularly and its use by subjects overseen by specifically trained personnel to ensure maximum safety and comfort.

Pregnancy:

Subjects are warned not to rely on "time of the month" for contraception.

